### 7.3.3 Serious

An AE or suspected adverse reaction is considered *serious* if, in the view of either the investigator or sponsor, it results in any of the following outcomes:

- Death
- Life-threatening AE
- Inpatient hospitalization or prolongation of existing hospitalization
- A persistent or significant incapacity or substantial disruption of the ability to conduct normal life function
- Congenital anomaly/birth defect

Important medical events that may not result in death, are life threatening, or require hospitalization may be considered serious when, based upon appropriate medical judgment, they may jeopardize the patient or participant and may require medical or surgical intervention to prevent one of the outcomes listed in this definition. Examples of such medical events include allergic bronchospasm requiring intensive treatment in an emergency room or at home, blood dyscrasias or convulsions that do not result in inpatient hospitalization, or the development of drug dependency or drug abuse.

It is important to distinguish between serious and severe AEs. Severity is a measure of intensity whereas seriousness is defined earlier in this section. An AE of severe intensity need not necessarily be considered serious. For example, nausea that persists for several hours may be considered severe nausea, but not a SAE unless it meets the criteria shown above. On the other hand, a stroke that results in only a limited degree of disability may be considered a mild stroke but would be a SAE when it satisfies the criteria shown above.

The causality of SAEs (their relationship to all study treatment/procedures) will be assessed by the investigator(s) and communicated to the study sponsors in accordance with the agreed process.

### 7.3.4 Life threatening

An AE or suspected adverse reaction is considered *life threatening* if, in the view of either the investigator or sponsor, its occurrence places the patient or participant at immediate risk of death. It does not include an AE or suspected adverse reaction that, had it occurred in a more severe form, might have caused death.

### 7.3.5 Overdose

A maximum tolerated dose has not been established for osimertinib. An overdose is any dose which exceeds the daily dose that is defined in the clinical study protocol.

There is no specific treatment in the event of osimertinib overdose, and symptoms of overdose are not established. In the event of an overdose, physicians should follow general supportive measures and should treat symptomatically.

For overdoses associated with a SAE, the standard agreed reporting timelines apply.

### 7.3.6 Maternal and Paternal Exposures

#### **Maternal Exposure**

If a participant becomes pregnant during the course of the study, osimertinib should be discontinued immediately.

Pregnancy itself is not regarded as an AE unless there is a suspicion that the IP under study may have interfered with the effectiveness of a contraceptive medication. Congenital abnormalities/birth defects and spontaneous miscarriages should be reported and handled as SAEs. Elective abortions without complications should not be handled as AEs. The outcome of all pregnancies (spontaneous miscarriage, elective termination, ectopic pregnancy, normal birth or congenital abnormality) should be followed up and documented even if the participant was discontinued from the study.

If any pregnancy occurs in the course of the study and within 6 weeks of the last dose of osimertinib, then the Investigator or other site personnel informs the appropriate sponsor representatives within 1 day i.e., immediately but **no later than 24 hours** of when he or she becomes aware of it.

The same timelines apply when outcome information is available.

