## 3 Study Design

### 3.1 Characteristics

This is a Phase 2, single arm, open-label, multicenter study evaluating the safety and efficacy of osimertinib administered orally daily to patients with stage I-IIIa, EGFR-mutant NSCLC who are planning to undergo surgical resection of their cancer.

Patients will undergo a research biopsy for correlative studies during screening prior to starting osimertinib treatment. Treatment will consist of osimertinib 80 mg by mouth daily in 28 day cycles given as neoadjuvant therapy. Patients may receive a second cycle of osimertinib at investigator's discretion. Patients will undergo serial assessments for anti-tumor efficacy and drug safety. The last dose of study drug will occur 3-7 days prior to planned surgical resection, which will occur within 14 days of the patient's most recent disease assessment scan.

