    - Platelets  $> 100,000/\text{mCL}$
  - Renal Function: CrCl  $> 50$  mL/min for patients with SCr  $> 1.5 \times$  ULN.
12. Ability to swallow oral medications
13. Women of childbearing potential must have a negative serum pregnancy test within 3 days prior to the first dose of study treatment and agree to use highly effective contraception, during the study and for 90 days following the last dose of osimertinib
  - Women of Childbearing Potential (WoCBP): Women between menarche and menopause who have not been permanently or surgically sterilized and are capable of procreation.
  - Women NOT of Childbearing Potential: Women who are permanently or surgically sterilized or postmenopausal (definitions below):
    - Permanent sterilization includes hysterectomy and/or bilateral oophorectomy and/or bilateral salpingectomy but excludes bilateral tubal occlusion. Tubal occlusion is considered a highly effective method of birth control but does not absolutely exclude possibility of pregnancy. (The term occlusion refers to both occluding and ligating techniques that do not physically remove the oviducts).
      - Women who have undergone tubal occlusion should be managed on trials as if they are WoCBP (e.g. undergo pregnancy testing etc., as required by the study protocol)
      - Women will be considered postmenopausal if they are amenorrhoeic for 12 months without an alternative medical cause. The following age-specific requirements apply:
        - Women under 50 years old will be considered postmenopausal if they have been amenorrhoeic for 12 months or more following cessation of exogenous hormonal treatments and with luteinizing hormone and follicle-stimulating hormone levels in the postmenopausal range
        - Women over 50 years of age will be considered postmenopausal if they have been amenorrhoeic for 12 months or more following

cessation of all exogenous hormonal treatments

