#### 6.1.4 End-of-Treatment Study Procedures

To be completed at 30 days of post-operative D15 study visit.

- Physical examination
- Vital signs
- Performance Status
- Evaluation of AEs
- Concomitant medications
- CBC with differential and platelet count
- Blood chemistry assessment, including:
  - ALP, ALT/AST, total bilirubin, calcium, phosphorus, BUN, creatinine, total protein, albumin, fasting or non-fasting glucose, potassium, sodium, chloride, bicarbonate
- Coagulation assessment, including PT/PTT/INR
- Urinalysis
- Serum or urine pregnancy test
- Electrocardiogram (ECG)
- Peripheral blood collection for exploratory biomarker analysis

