#### 6.1.5 Long Term/Survival Follow-up Procedures

Patients will continue to be followed as per standard of care every three months (+/- 2 weeks) following the end-of-treatment visit for a period of up to one 5 years, or until death or closure of the study. This follow up will include assessment of survival status and subsequent therapies for NSCLC. Standard of care tumor scans (CT chest/abdomen/pelvis or PET/CT) will occur every 6 months, unless local requirements or investigator opinion warrant more frequent scans. After the first year, assessment of survival status and subsequent therapies will occur via telephone or via routine clinic visits every six months (+/- 2 weeks) for 5 years post-surgery.

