## **6.6 Contraceptive Counseling**

1. Females of child-bearing potential should use reliable methods of contraception from the time of screening until 3 months after discontinuing osimertinib. Acceptable methods of contraception are described in Section 3.3.1.

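### On its plain reading, 24-hour pregnancy notification covers only pregnancies up to 6 weeks after the last dose, while contraception is required for 90 days; no listed contact after the end-of-treatment visit asks about pregnancy

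*Combined protocol and SAP*

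**What the plan says.** **At-risk period.** Section 3.3.1, criterion 13, has women of childbearing potential "agree to use highly effective contraception, during the study and for 90 days following the last dose of osimertinib". Section 6.6 asks for contraception "from the time of screening until 3 months after discontinuing osimertinib".

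**Notification.** Section 7.3.6 (Maternal Exposure) gives the site 24 hours from awareness to inform the sponsor, under the condition "If any pregnancy occurs in the course of the study and within 6 weeks of the last dose of osimertinib".

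**Outcomes.** The same section says that the outcome of every maternal pregnancy "should be followed up and documented even if the participant was discontinued from the study". It adds: "Congenital abnormalities/birth defects and spontaneous miscarriages should be reported and handled as SAEs". Neither sentence has a day limit. Section 7.7 (reporting to the companies supplying drug) runs routine AE and SAE collection through a 30-day follow-up period. After withdrawal from treatment, collection runs for 30 days from the last dose and/or until the event resolves.

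**Detection.** Section 3.1: "The last dose of study drug will occur 3-7 days prior to planned surgical resection". The last listed pregnancy test is at the end-of-treatment visit, timed in Section 6.1.4 as "To be completed at 30 days of post-operative D15 study visit". Of the later contacts, Section 6.1.5 says "This follow up will include assessment of survival status and subsequent therapies for NSCLC" and adds standard-of-care scans. In Appendix 1 the long-term column is marked only for survival and therapies and for imaging, and footnote 17 is consistent with that.

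**The concern.** The protocol asks women to avoid pregnancy for 90 days after the last dose, so it treats those 90 days as a period of possible risk. The rule that gets a pregnancy to the sponsor promptly appears to cover fewer than half of them. For a pregnancy that begins in weeks 7-13, the site has no clear 24-hour duty, and after the end-of-treatment visit nothing on the schedule prompts it to ask.

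The protections without a day limit (outcome follow-up, and SAE handling of miscarriages and birth defects) start only once the site knows. A miscarriage or birth defect from such a pregnancy would also usually come after the 30-day collection period in Section 7.7, and the protocol does not say which provision governs. What is at stake is the completeness and speed of pregnancy safety reporting.

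**Working it through.** The plan gives no figure of its own to reproduce. The check is day arithmetic, counted from the last dose.

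**1. Notification window against contraception period**
- Notification: 6 weeks × 7 = 42 days (Section 7.3.6).
- Contraception: 90 days (criterion 13).
- Not covered: 90 − 42 = 48 days (days 43-90); 48/90 = 53%.
- With the 3 months of Section 6.6 taken as 89-92 days: 47-50 days.

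**2. Last scheduled pregnancy test, patients who have surgery**
- The last dose is 3-7 days before surgery. The end-of-treatment visit is 15 + 30 = 45 days after surgery.
- Nominal test day: 3 + 45 = 48 to 7 + 45 = 52.
- Remaining to day 90: 90 − 52 = 38 to 90 − 48 = 42 days (42-47%).
- With the ±3-day window used on both the day-15 and the end-of-treatment visits: day 48 − 6 = 42 to 52 + 6 = 58, leaving 32-48 days.
- The test is therefore nominally after day 42 and covers part of the period, but it cannot detect a later conception.

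**3. First contact after that visit**
- Three months taken as 91 days, ±14 days: 48 + 91 − 14 = day 125 to 52 + 91 + 14 = day 157 (139-143 without the window).
- Earliest with every window used: 42 + 91 − 14 = day 119, which is 29 days after day 90.
- A question asked there always follows the whole 90-day period.

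**4. How the gap depends on the reading of Section 7.3.6**

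| Reading | Notification covers pregnancies up to | Gap to day 90 |
|---|---|---|
| Both conditions must hold | day 42 | 48 days |
| Conditions additive; study ends at end-of-treatment visit | about day 48-52 | 38-42 days |
| Conditions additive; study includes 5-year follow-up | end of follow-up | none, except for women who leave early (48 days) |

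**5. Drug remaining at day 42**
- Mean half-life 48 hours (Section 4.1.1, Metabolism): 42 × 24 / 48 = 21 half-lives of parent drug. Half-lives of the two active metabolites are not given.

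**The case against.** **The wording may be additive.** Criterion 13 joins the study and a post-dose period additively, and Section 3.5 follows all patients for relapse and survival for up to 5 years. Read that way, Section 7.3.6 leaves almost no gap. This stands as a possible reading, so the 48 days cannot be stated as certain. But it leaves the 6-week phrase with work to do only for women who leave early. Criterion 13 also seems to use the word study more narrowly, since 90 days after the last dose would add little to a 5-year period.

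**The two periods need not match.** Contraception is a precaution and expedited notice is a reporting trigger; no section says they must be equal. For men they differ too: 120 days of contraception (criterion 14) against partner-pregnancy outcome follow-up for conceptions up to 6 months after dosing. That is true, but the men's follow-up window exceeds the contraception period and is dated by conception. The duties differ, so this is only a comparison.

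**Stronger readings that a reader might infer, and that the documents do not support:**
- *That the duty to report stops at day 42.* The 6 weeks limits when the pregnancy occurs; the 24 hours runs from awareness. A pregnancy within the window but found later must still be notified.
- *That later pregnancies get no follow-up.* Section 7.3.6 follows the outcome of all of them, without a day limit.
- *That pregnancies in weeks 7-13 are meaningfully exposed to drug.* After about 21 half-lives little parent drug should remain.
- *That the gap in detection can be sized for a woman who has no surgery.* Her end-of-treatment visit has no date, because it is counted from a post-operative visit, and safety follow-up runs 30 days from removal from study (Section 3.5). The documents do not give the removal date relative to the last dose. The 2-week limit in Table 5.3 concerns going off protocol therapy, not leaving the study.

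**Conclusion.** The point holds as a minor safety-reporting inconsistency. On its plain reading Section 7.3.6 leaves 48 of the protocol's own 90 days (53%) without a clear 24-hour notification duty. Under the other readings the gap is 38-42 days, or close to nothing, and the text does not settle which applies. For patients who have surgery, 38-42 days of the period follow the last scheduled test (32-48 with visit windows), and no listed contact afterwards asks about pregnancy.

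The practical effect is small. The number of women of childbearing potential among the 27 patients is not given and is likely to be low, possibly zero. No efficacy endpoint is affected. The case for change rests on clarity and low cost, not on evidence of harm.

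**What to change.** 1. **Section 7.3.6.** Replace the window with: *any pregnancy ongoing at the first dose, or with conception at any time from then until at least 90 days after the last dose of osimertinib, including in women who leave the study early, whenever the site becomes aware of it.* Keep the 24-hour limit from awareness. Including pregnancies ongoing at the first dose matters because a conception shortly before day 1 could be missed by the pre-dose test and be exposed from the start. If the sponsor means the duty to run through the 5-year follow-up, it should state that later end date.
2. **Section 7.3.6, added sentence.** A miscarriage or birth defect from such a pregnancy is reported as an SAE regardless of the 30-day collection period in Section 7.7.
3. **Section 6.1.5 and Appendix 1.** Add a pregnancy question for women of childbearing potential at the existing first 3-month follow-up contact. For a woman who has no surgery, ask it at the first contact after day 90. The question detects a pregnancy only in retrospect, but it does cover the whole period.

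The cost is a wording amendment and one added question, with no extra visit or test.

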#### **Paternal Exposure**

Pregnancy of the participant's partners is not considered to be an AE. However, the outcome of all pregnancies (spontaneous miscarriage, elective termination, ectopic pregnancy, normal birth or congenital abnormality) should if possible be followed up and documented.

To capture information about a pregnancy from the partner of a male participant, the male participant's partner's consent must be obtained to collect information related to the pregnancy and outcome; the male participant should not be asked to provide this information. A consent form specific to this situation must be used. The outcome of any conception occurring from the date of the first dose until 6 months after dosing ends should be followed up and documented.

### 7.3.7 Disease progression

PD can be considered as a worsening of a participant's condition attributable to the disease for which the IP is being studied. It may be an increase in the severity of the disease under study and/or increases in the symptoms of the disease. The development of new, or progression of existing metastasis to the primary cancer under study should be considered as PD and not an AE. Events, which are unequivocally due to PD, should not be reported as an AE during the study.

### 7.3.8 New cancers

The development of a new primary cancer should be regarded as an AE and will generally meet at least one of the serious criteria. New primary cancers are those that are not the primary

reason for the administration of the study treatment and have developed after the inclusion of the patient into the study. They do not include metastases of the original cancer. Symptoms of metastasis or the metastasis itself should not be reported as an AE/SAE, as they are considered to be PD.

### 7.3.9 Lack of efficacy

When there is progression or deterioration related to NSCLC, there may be uncertainty as to whether this is lack of efficacy or an AE. In such cases, unless the Sponsor or the reporting physician considers that the study treatment contributed to the deterioration of the condition, or local regulations state to the contrary, the deterioration should be considered to be a lack of efficacy and not an AE.

### 7.3.10 Deaths

All deaths that occur during the study, or within the protocol-defined 30-day post-study follow-up period after the administration of the last dose of study treatment, must be reported as follows:

- Death that is clearly the result of PD should be reported to the study monitor at the next monitoring visit and should be documented in the eCRF but should not be reported as an SAE.
- Where death is not due (or not clearly due) to progression of the disease under study, the AE causing the death must be reported to the study monitor as a SAE within **24 hours** (see Section 7.2.2.3 for further details). The report should contain a comment regarding the co-involvement of progression of disease, if appropriate, and should assign main and contributory causes of death. This information can be captured in the eCRF.
- Deaths with an unknown cause should always be reported as a SAE. A post mortem maybe helpful in the assessment of the cause of death, and if performed, a copy of the post-mortem results should be forwarded to the study sponsors within the usual timeframes.

## 7.4 Recording of an Adverse Event

All grade 3 and above AEs will be entered into OnCore®, whether or not the event is believed to be associated with use of the study drug. Data about these events and their severity will be recorded using the NCI CTCAE v4.03.

The Investigator will assign attribution of the possible association of the event with use of the investigational drug, and this information will be entered into OnCore® using the classification system listed below:

Relationship	Attribution	Description
Unrelated to investigational drug/intervention	Unrelated	The AE is clearly NOT related to the intervention
	Unlikely	The AE is doubtfully related to the intervention
Related to investigational drug/intervention	Possible	The AE may be related to the intervention
	Probable	The AE is likely related to the intervention
	Definite	The AE is clearly related to the intervention

Signs or symptoms reported as AEs will be graded and recorded by the Investigator according to the CTCAE. When specific AEs are not listed in the CTCAE, they will be graded by the Investigator as none, mild, moderate or severe according to the following grades and definitions:

- Grade 0: No AE (or within normal limits)
- Grade 1: Mild; asymptomatic or mild symptoms; clinical or diagnostic observations only; intervention not indicated
- Grade 2: Moderate; minimal, local, or noninvasive intervention (e.g., packing, cautery) indicated; limiting age-appropriate instrumental activities of daily living (ADL)
- Grade 3: Severe or medically significant but not immediately life-threatening; hospitalization or prolongation of hospitalization indicated; disabling; limiting self-care ADL
- Grade 4: Life-threatening consequences; urgent intervention indicated
- Grade 5: Death related to AE

### 7.5 Follow-up of Adverse Events

All AEs will be followed with appropriate medical management until resolved. Patients removed from study for unacceptable AEs will be followed until resolution or stabilization of the AE. For AEs that do not require permanent discontinuation after stopping administration of the study drug, a re-challenge of the participant may be conducted if considered both safe and ethical by the investigator.

### 7.6 Adverse Events Monitoring

All AEs, whether or not unexpected, and whether or not considered to be associated with the use of the study drug, will be entered into OnCore®, as noted above.

The Investigator will assess all AEs and determine reportability requirements to the UCSF DSMC and UCSF's IRB; and, when the study is conducted under an Investigational New Drug (IND) Application, to the FDA if it meets the FDA reporting criteria.

All AEs entered into OnCore® will be reviewed by the HDFCCC Site Committee on a monthly basis. The Site Committee will review and discuss the selected toxicity, the toxicity grade, and the attribution of relationship of the AE to the administration of the study drug(s).

In addition, all AEs and suspected adverse reactions considered "serious" that are entered into OnCore® will be reviewed and monitored by the DSMC on an ongoing basis. They will be discussed at DSMC meetings, which take place every six (6) weeks.

For a detailed description of the Data and Safety Monitoring Plan (DSMP) for a Multicenter Phase 2 or 3 Institutional Study at the HDFCCC, please refer to Appendix 3 DSMP\* for Phase II/III Multicenter Institutional Studies.

### 7.7 Expedited Reporting

#### **Reporting to the DSMC**

If a death occurs during the treatment phase of the study or within 30 days after the last administration of the study drug(s) and it is determined to be related either to the study drug(s) or to a study procedure, the Investigator or his/her designee must notify the DSMC Chair (or qualified alternate) within 1 business day of knowledge of the event. The contact may be by phone or e-mail.

